- 230 10 Baselin e Desa i ptive Statistics
- 231 Baseline demographic and clinical characteristics of all participants included in the primary analysis will
- be summarized in a table using summary statistics appropriate to the distribution of each variable.
- 233 Characteristicswill include:
- 234 Age
- Diabetes duration
- BMI percentile
- 237 Sex
- Race/ethnicity
- Parents' highest education level
- Annual household income
- Health insurance
- HbAlc at initiation of closed loop use
- Insulin modality
- Total daily insulin (units/kg)
- Number of injections of short-acting insulin per day
- Number of diabetic ketoacidosis events in the past 12 months
- Number of severe hypoglycemia events in the past 12 months

248 11 DeviceIssues

- 249 The following will be tabulated for the 8-week study period to assess device issues:
- Device malfunctions requiring study team contact and other reported device issues
- Rate of different failure events and alarms per 24 hours recorded by the Control-IQ system
- 252 Tabulations will include all events that occur between enrollment and the 3-Day Post-Study Safety

contact or the end of the 71" day after the date of the Closed Loop Initiation visit- whichever is earlier.

- 254 Details of device issues will be provided in a listing.
- 255 **12 Planned Inteli m** An al yses
- 256 No formal interim efficacy analyses are planned.
- 257 The DSMB will review safety data at intervals, with no formal stopping rules.
- 258 13 Subgroup Analyses
- 259 With only 30 participants, the ability to evaluate subgroups is limited. However, percentage of timespent
- 260 > 250 mg/dL and% of timespent <54 mg/dL over 8 weeks will be explored separately in baseline HbAlc,
- 261 race/ethnici,ty MDI or pump use at enrollment, and sex. No p-values will be calculated for these analyses.

JAEBCENTER FORHEALTH RESEARCH

262 14 Missing Data

263 All comparisons will be restricted to available cases.

264 15 Multiple Compa1isons/Multiplicity

- 265 For the baseline versus follow-up comparisons of the metrics mentioned in 6.1, the overall type I error
- will be preserved using the hierarchical procedure described above. For all other analys, es the false
- discovery rate will be controlled using the adaptive Benjamini-Hochberg procedure.¹ The categories for
 the FDR correction will be:
- Baseline vs follow-up for CGM-measured endpoints
- Baseline vs follow-up for insulin endpoints
- PEDAP-AI vs PEDAP for CGM-measured endpoints

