## 222 Table 4-1. Study Visits

| Target Day/Week                 | Contact Type  | Target/Allowable Window
(around Target Day/Week) |
|---------------------------------|---------------------------|---|
| 3 days                          | VC/V                      | $\pm 1 \text{ day}$                                 |
| 1 week                          | VC/V                      | $\pm 2 \text{ days}$                                |
| 2 weeks                         | VC/V                      | $\pm 2 \text{ days}$                                |
| 4 weeks                         | VC/V                      | $\pm 4 \text{ days}$                                |
| 6 weeks                         | VC/V                      | $\pm 4 \text{ days}$                                |
| 8 weeks                         | VC/V                      | $\pm 4 \text{ days}$                                |
| 3-day post-study safety contact | VC/P                      | $\pm 1 \text{ day}$                                 |

 Contact Types are defined as Clinic Visit (V), Videoconference (VC), or Phone call (P); Phone calls may be replaced by

224 Videoconferences or Clinic Visits and Videoconferences may be replaced by Clinic Visits at investigator discretion

225

219

226 Additional office visits may occur as needed.

227

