## 8.10 Comparison with PEDAP Historical Control

974 Results from this PEDAP-AI study will be compared with those from a sample of participants from the 975 prior PEDAP study. For this analysis, participants from the prior PEDAP study will be limited to those who were using MDI before initiating use of the study pump, and whose baseline HbA1c values are no 976

more than 0.2 percentage points outside of the range observed among the PEDAP-AI participants. These 977

- 978 comparisons will be restricted to a follow-up period of approximately two weeks. For PEDAP-AI
- 979 participants, this will be the period from the adjustment of pump settings at the 6-Week visit until the
- beginning of the day of the 8-Week visit. For the PEDAP historical control group, the follow-up metrics 980
- will be calculated from RCT study phase data for those who were assigned to the CLC group, and 981
- Extension phase data for those who were assigned to the SC group. In either case, follow-up data will 982
- come from the 14 days prior to the 56th day after the date of closed loop initiation. 983
- Comparisons between the PEDAP-AI group and the PEDAP historical control group will be made for all 984 985 of the hierarchical and secondary efficacy endpoints listed in section 8.4.2. Continuous endpoints will be
- compared between the PEDAP-AI and PEDAP cohorts using a linear model adjusting for the baseline 986

value, age at initiation of closed loop use, and clinical center as fixed effects. Binary endpoints will be

compared using a logistic model that adjusts for the same effects. Summary statistics for baseline, follow-

- 989 up, and change from baseline will be reported by study, along with the adjusted differences between the
- studies and their 95% confidence intervals. Boxplots displaying baseline and follow-up for both groups
- 991 will be drawn for continuous outcomes.

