prior PEDAP study. For this analysis, participants from the prior PEDAP study will be limited to those 118

- 119 whose RCT baseline HbAlc values are no more than 0.2 percentage points outside of the range observed
- 120 among the PEDAP-AI participants. Basdine metrics for the PEDAP historical control group will be as
- reported for the PEDAP RCT. 121
- The follow-up period for these comparisons will be the7m and gm weeks of study pump use. For PEDAP-122
- 123 AI participa, ntsthis will be the period from the adjustment of pump settings at the 6-Week visit until the
- end of the day before the 8-Week visit. If the 6-Week visit is missed, data from the 14 days before the 8-124
- Week visit will be used. PEDAP-AI participants will be excluded from these analyses if they miss the 8-125
- 126 Week visit. For the PEDAP historical control group, follow-up metrics will be calculated from the 14
- daysprior to the 56m day after the date of the beginning of study pump use. These data will come from the 127
- RCT phase for those who were assigned to the CLC group and Extension phase for those who were 128
- 129 assigned to the SC group. Participantsmust have spent at least SO% of the time between pump initiation and the end of the follow-up period in closed-loopmode, and provided at least 168 hours of data in both
- 130
- the baseline and follow-up periods for inclusion in analyses. 131
- 132 Baseline insulin metrics will usedata reported from the Diabetes Screening CRF. Insulin data must be
- 133 presenton at least 70% of follow-up days to calculate insulin metrics. The day of the 6-Weekvisit will be
- excluded from the calculation of PEDAP-AI participants' insulin metrics. Calculation of units/kg will use 134
- 135 the weight from the Screening visit only.
- 136 5.7 Analysis \Vindows

137 For any analysis or tabulation that involves HbAlc measured at the Closed Loop Initiation visit, the 138 sample must be collected no earlier than three daysprior to the visit and no later than 21 days after the 139 visit.

140 6 Analysis

141 Analysis of the Hiera rchicalEndpoints 6.1

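### In the PEDAP comparison, trial children's follow-up window can run from 6 to 22 days against a fixed 14 for controls, and the 168-hour rule can exclude a child whose visits were all on time

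*SAP*

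**What the plan says.** SAP 5.6 sets the follow-up for the historical comparison as the seventh and eighth weeks of study pump use, and Protocol 8.10 describes it as about two weeks. The operative definitions differ by cohort.

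- **Trial children.** The window "will be the period from the adjustment of pump settings at the 6-Week visit until the" close of the calendar day preceding the 8-Week visit. For a child who did not attend at 6 weeks, a fixed look-back of 14 days from the 8-Week visit replaces it. That fallback is tied to a missed 6-Week visit, not to a short gap. A child who misses the 8-Week visit is excluded.
- **Historical controls.** Their "follow-up metrics will be calculated from the 14" days before day 56, whatever their visit dates.
- **Inclusion, both cohorts.** Participants must have spent at least half the time in closed loop "and provided at least 168 hours of data in both" the baseline and follow-up periods.
- **Visit windows.** Protocol Table 4-1 allows 4 days either side of target for the 6-week and 8-week visits, and sets no minimum interval between them.
- **Control anchor.** In Protocol 8.10 the control data "come from the 14 days prior to the 56"th day after closed loop initiation. SAP 5.6 counts instead from the beginning of study pump use.

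**The concern.** The SAP names a two-week period but ties it, for one cohort only, to two visit dates that can each move by 4 days. An absolute data minimum is then applied to a window of variable length. Two consequences follow.

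First, a child can attend both visits within the allowed windows, wear the CGM throughout, and still be unable to supply the required hours. A child who skips the 6-Week visit is given 14 days and can stay in, so attending can cost a child its place in the comparison.

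Second, the cohorts are not measured over the same length of time. Each trial child's mean carries more or less noise according to scheduling, whereas every control's rests on a 14-day window. All hierarchical and secondary efficacy endpoints go into this comparison (SAP 6.2.2), and the planned model has no term for window length.

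**Working it through.** **Inputs.** 6-Week visit on days 38 to 46 (42 ± 4) and 8-Week visit on days 52 to 60 (56 ± 4), from Protocol Table 4-1. Window definitions and the 168-hour minimum, from SAP 5.6. The clock time of the adjustment is not given, so it is varied.

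**Formula.** Hours available = 24 × (day of 8-Week visit − day of 6-Week visit) − clock hour of the adjustment.

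**The plan's own figure.** On target days, 24 × (56 − 42) = 336 hours, or 14.0 days, at most. With a 10:00 adjustment it is 326 hours, or 13.6 days. The stated two weeks reproduces.

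**Range for on-time visits.** Shortest gap: 52 − 46 = 6 days, at most 144 hours. Longest: 60 − 38 = 22 days, at most 528 hours. The day-59 cap in SAP 5.4 is not repeated in 5.6, but would not bind here, because a day-60 visit already ends the window on day 59.

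**Wear needed to reach 168 hours** (168 ÷ hours available):

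| Window | Midnight adjustment | 08:00 | 17:00 |
|---|---|---|---|
| 6-day gap | impossible (144 h) | impossible (136 h) | impossible (127 h) |
| 7-day gap | 100% (168 h) | impossible (160 h) | impossible (151 h) |
| 8-day gap | 87.5% | 91.3% | 96.0% |
| 14-day gap | 50.0% | 51.2% | 52.7% |
| 22-day gap | 31.8% | 32.3% | 32.9% |
| Controls, fixed 14 days | 50% | 50% | 50% |

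**Forced exclusions.** There are 9 × 9 = 81 in-window day pairs. One has a 6-day gap (46/52) and two have a 7-day gap (46/53 and 45/52), so 3 of 81 cannot in practice qualify.

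**Turning the count into children.** The documents give no distribution of visit dates, so two are assumed. Capture below 100% is also assumed, with a midday adjustment: the child fails if (gap − 0.5) × 24 × capture < 168. In the clustered case each visit's deviation of d days from target has weight proportional to exp(−d²/4.5), that is, an SD parameter of 1.5 days.

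| CGM capture | Gaps that fail | Visits spread evenly | Of 30 | Visits clustered on target | Of 30 |
|---|---|---|---|---|---|
| 100% | up to 7 days | 3/81 = 3.7% | 1.1 | 0.06% | 0.02 |
| 90% | up to 8 days | 6/81 = 7.4% | 2.2 | 0.36% | 0.1 |
| 80% | up to 9 days | 10/81 = 12.3% | 3.7 | 1.5% | 0.4 |

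Gaps outside 12 to 16 days make up 42/81 = 52% under even spread and 23% under clustering.

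**Precision.** Assume a day-to-day SD of time in range of 10 to 15 points and independent days. The SE of one child's mean is SD ÷ √days: 4.1 to 6.1 points at 6 days, 2.7 to 4.0 at 14, and 2.1 to 3.2 at 22.

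**Threshold endpoints.** The mean gap over the 81 pairs is exactly 14 days. Take gaps of 8 days or more, evenly spread, with (gap − 0.5) days of data. The average of 1/days is then about 9% above 1/14, so within-child follow-up variance rises by about 9%. Assume further a between-child SD of change of 8 to 12 points and a true mean change of 0 to 15 points. The proportion reaching a gain of 5 or 10 points then differs from the fixed 14-day figure by less than 0.2 percentage points, or under 0.002 × 30 = 0.06 of a child.

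**The case against.** The visit-based window has a purpose. It confines the trial children's data to the settings in force after the last AI-driven adjustment, with the same start as the sixth adaptation period in SAP 6.4. A fixed look-back would mix in earlier settings. Forced exclusion needs a late 6-Week visit followed by an early 8-Week visit, which is rare if visits cluster on target. Children excluded here still contribute to the baseline comparisons, which use the whole treatment period (SAP 5.4 and 6.1). The historical comparison lies outside the hierarchy, under false discovery rate control (SAP 15), in a pilot that is not formally powered (SAP 4).

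All of that stands, and it limits the size of the point. It does not explain why an on-time child should be dropped while one who missed a visit is kept. Nor does it explain an absolute hours rule here, when SAP 6.4 uses a proportional one (75% of the period) for its variable-length periods.

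A reader might infer three stronger things that the documents do not support:

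- **That unequal windows materially distort the responder endpoints.** For a single child with no true gain, noise alone crosses the 5-point threshold about 11 to 21% of the time on 6 days and 3 to 11% on 14 days (same SDs, baseline error ignored). Averaged over the possible gaps, with realistic spread between children, the shift is negligible on the assumptions above.
- **That trial children should simply be given the controls' window ending at day 56.** An on-time 8-Week visit can fall on days 52 to 55. At that visit the child moves to post-study therapy (Protocol 3.3.2) and returns the pump and CGM (Protocol 4.4). Up to 4 days of that window would follow the end of study device use.
- **That study pump use is the wrong anchor for controls.** Protocol 3.3.1 times the first trial visit from the start of pump use, and SAP 5.6 counts its weeks the same way. The documents disagree on the anchor but do not show which one should go.

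**Conclusion.** The point holds in a limited form. The 6-to-22-day range and the 3-of-81 count follow directly from the visit windows and the 168-hour rule. They need only the assumption that the adjustment is not made at midnight. The exclusion of an on-time child beside the retention of one who missed the 6-Week visit is a defect in the wording.

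The likely effect is small. With full wear it is about one child in 30 if visits were spread evenly over their windows, and close to none if they cluster on target. With 80 to 90% capture, about 2 to 4 children could be lost under even spread, but fewer than one under clustering. Those figures rest on assumed visit dates and capture rates. Uneven precision between cohorts is real. No material shift in the threshold endpoints has been shown.

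The difference in control anchor between Protocol 8.10 and SAP 5.6 is a separate inconsistency. Protocol 3.2 allows open-loop use of the study pump before closed loop starts, so the two dates can differ for trial children. Whether they differ for controls cannot be seen in these documents.

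**What to change.** In SAP 5.6, extend the existing fallback, the 14 days before the 8-Week visit. At the least, apply it whenever the gap between the two visits is too short to supply 168 hours. Preferably, apply it to every trial child who attends the 8-Week visit. Each child then has 14 × 24 = 336 hours available, 168 hours means 50% coverage as for controls, and visit timing alone cannot exclude anyone. Report the visit-to-visit window as a sensitivity analysis. Do not end the trial children's window at day 56.

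Separately, choose one anchor for the control window and state it identically in Protocol 8.10 and SAP 5.6.

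The cost is wording only, on data already collected. The price is that in short-gap children some days come before the 6-week settings change: 14 − 6 = 8 of the 14 days at worst. If the rule is applied to all, 36 of the 81 day pairs (gaps of 6 to 13 days) include at least one such day. The sensitivity analysis will show whether that matters.

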# **3.2.2 t:connect Mobile App for Data Upload to Study Server**

287 The participant/parent will be expected to upload pump and CGM data at least once per day during the

course of the main phase of the study. This data upload will be achieved using the t:connect Mobile App,

which will be installed on the participant/parent's personal phone. Participants/parents will be trained on

configuring the app to connect to a study-provided t:connect account and ensuring that pump data upload

to t:connect at least once per day.

286

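### SAP 5.6 drops PEDAP-AI children who miss the 8-Week visit from the historical comparison, even with adequate data, and sets no matching visit condition for the PEDAP controls

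*SAP*

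**What the plan says.** SAP 5.6 defines who enters the comparison with the PEDAP historical control group and over which days.

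- **PEDAP-AI window.** It runs from the settings adjustment at the 6-Week visit to the end of the day before the 8-Week visit. A missed 6-Week visit has a fallback: "If the 6-Week visit is missed, data from the 14 days before the" 8-Week visit. A missed 8-Week visit has none: "PEDAP-AI participants will be excluded from these analyses if they miss the" 8-Week visit.
- **Control window.** "For the PEDAP historical control group, follow-up metrics will be calculated from the 14" days before day 56 of study pump use. The data come from the "RCT phase for those who were assigned to the CLC group and Extension phase for those who were" assigned to standard care. No attendance condition is stated.
- **Filters not tied to a cohort.** "Participantsmust have spent at least SO% of the time between pump initiation" and the end of follow-up in closed-loop mode (SO% is a scanning error for 50%), and must have "provided at least 168 hours of data in both" the baseline and follow-up periods.
- **Control-only filter.** RCT baseline HbA1c must lie no more than 0.2 percentage points outside the PEDAP-AI range.

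Protocol 3.2.2 describes how the data arrive: "The participant/parent will be expected to upload pump and CGM data at least once per day during the" main phase. Protocol 4.1.1 adds that t:connect data pass to the Clinician Portal automatically every few hours.

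**The concern.** A child can have adequate pump and CGM data for weeks 7 and 8 and still be left out because a visit did not take place. A PEDAP control with the same data is kept. Children who miss a final visit may differ from those who attend, and the rule acts on one side only.

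This is the only planned comparison with children who used the system without AI-driven settings, and SAP 6.2.2 applies it to every hierarchical and secondary efficacy endpoint. Its model adjusts for baseline value, age, prior pump or MDI use and clinical center, but not for adherence. SAP 14 restricts comparisons to available cases, and no sensitivity analysis brings the excluded children back. With about 30 children, each exclusion carries weight.

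**Working it through.** The plan states no expected number of missed visits, effect size or standard deviation, so it has no figure of its own to reproduce. The check has two parts.

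**1. Inclusion rules side by side (SAP 5.6)**

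| Condition | PEDAP-AI | PEDAP controls |
|---|---|---|
| At least 50% closed-loop time | yes | yes |
| At least 168 h at baseline and in follow-up | yes | yes |
| HbA1c close to the PEDAP-AI range | reference | yes |
| Extension-phase data needed | no | yes, if assigned to standard care |
| 8-Week visit attended | **yes** | **no** |

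The 168-hour rule requires 168 / 336 = 50% of a 14-day window. In a window that starts at day 42, a child needs data to at least day 42 + 168/24 = day 49. A child who stops earlier fails in either cohort, whatever happens with the visit. The visit rule therefore changes the analysis set only for a PEDAP-AI child who passes the shared filters and then misses the visit.

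For example, suppose two children stop on day 51, each with more than 168 hours since day 42 and adequate closed-loop use. The control is analysed; the PEDAP-AI child who misses the visit is not.

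Elsewhere the SAP copes without the visit. Section 5.4 substitutes the final contact date for non-completers and caps follow-up at day 59. Section 6.4 closes each of the first five adaptation periods at the latest in-window date when the next visit is missed. The same child can thus count against baseline in 6.1 and be absent from the historical comparison.

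**2. Illustrative size**

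Let n be the children otherwise eligible, m those dropped only by the visit rule, and d the attenders' mean minus the missers' mean. The shift in the unadjusted PEDAP-AI mean is (m / n) × d. Both m and d are assumptions. The value n = 30 is the target number of completers (SAP 4).

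| m of 30 | d = 5 points | d = 10 points | d = 15 points |
|---|---|---|---|
| 1 | 0.17 | 0.33 | 0.50 |
| 2 | 0.33 | 0.67 | 1.00 |
| 3 | 0.50 | 1.00 | 1.50 |

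If missers come on top of the 30 completers, n is larger and the shift smaller: with n = 35, the range for m = 1 to 3 is 0.14 to 1.29 points.

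For a binary endpoint with 15 of 30 responders and all missers non-responders, the rate rises by 15/(30 − m) − 15/30. That is 1.7, 3.6 and 5.6 percentage points for m = 1, 2 and 3.

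If nobody misses the visit, or missers do not differ from attenders, every figure is 0.

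**The case against.** The strongest case on the other side is that the affected group may be nearly empty. The 168-hour rule already removes early stoppers. The visit may be held remotely, has a window of ±4 days, and is when devices are returned and the child moves to post-study therapy. SAP 6.4 treats missed and out-of-window visits as different things, so a late visit need not count as missed. The comparison is also non-randomised and secondary, in a pilot that was not formally powered, and the flowchart in SAP 9 will show missed visits. All of this stands, and it limits the size of the problem. It does not give a reason for a visit condition in one cohort only.

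The rule may exist because the PEDAP-AI window ends at the visit and has no end date without it. That is a fair explanation, but the day-56 anchor used for controls supplies an end date.

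A reader might infer more than the documents support:

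- **That only PEDAP-AI is selected on adherence.** The 50% and 168-hour rules select on device use in both cohorts, and controls assigned to standard care also had to supply Extension-phase data. Only the visit condition is one-sided.
- **That every adjusted difference is biased in favour of PEDAP-AI.** The documents do not show that missers do worse. The endpoints include several hypoglycemia measures, on which missers need not do worse, and total daily insulin and percent basal, which have no favourable direction.
- **That the SAP contradicts the protocol.** Protocol 8.10 has no such exclusion, but its PEDAP-AI window also ends at the 8-Week visit, so it leaves the missed-visit case undefined.

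**Conclusion.** The point holds as a one-sided and avoidable selection rule. Beyond the shared filters, its only added effect is to discard PEDAP-AI children with adequate week 7 and 8 data. It can bias the historical comparison. For time in range the plausible direction favours PEDAP-AI, on the unverified assumption that children who miss the visit do worse.

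The illustrative shift is about 0.2 to 1.5 points in the unadjusted PEDAP-AI mean for 1 to 3 missers of 30 with time in range 5 to 15 points lower. This is not the bias of the planned adjusted difference, because whatever the covariates explain would be removed. The true effect may be small or zero. The baseline comparisons, including the primary non-inferiority tests, do not use this rule.

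**What to change.** In SAP 5.6:

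1. Delete the exclusion for a missed 8-Week visit.
2. When that visit is missed, use the 14 days before day 56 after closed-loop initiation, as for controls, and only data from while the study pump was in use. Protocol 8.10 counts the control window from closed-loop initiation and SAP 5.6 from the start of study pump use, so name one start for both cohorts.
3. Leave unchanged the 50% closed-loop rule, the 168-hour rule at baseline and in follow-up, and the HbA1c condition for controls.
4. Report how many PEDAP-AI children missed the visit and are included through this window.
5. As a sensitivity analysis, repeat the comparison with the day-56 window applied to all PEDAP-AI children.

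The cost is a short SAP edit and one extra run of the comparison; no new data are needed. The downside is that a day-anchored window is mixed with the visit-anchored one for the few children who miss the visit. The analysis in item 5 shows whether that matters.

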# **371 3.3.4 Unscheduled Visits**

Participants may have unscheduled visits during the study period if required for additional device training or other unanticipated needs per the study investigator discretion.

- During an unscheduled visit, the study investigator may elect to request an off-cycle optimization of pump
- settings from the UVA Clinician Portal and update the participant's pump settings accordingly.

376

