# 8.12 Additional Tabulations and Plots

Summary statistics will be tabulated by daytime (6:00 am - 9:59 pm) and nighttime (10:00 pm - 5:59 am) during baseline and the 8 weeks of follow-up for each of the continuous CGM-measured outcomes listed in section 8.4.2.

1003 During the trial period, the closed-loop system will include a periodic parameter adjustment driven by an

1004 AI-based Advisor system. Tabulations, 24-hour profile plots, and boxplots of the continuous CGM-

1005 measured outcomes listed in section 8.4.2 will be generated for each of the six adaptation periods and the 1006 two 4-week periods of the study.

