- 200 the second 4-weekperiod will be the end of the day before the 8-Week visit dateor the end of the 59th day
- after the date of the Closed Loop Initiation visit- which ever is earlier. This date will also serve as the end
- 202 of the sixth adaptation period, which will begin at the 6-Week visit. The other five adaptation periods will 203 include data from the adjustment of pump settings at the visit until the adjustment of pump settings at the
- subsequent visit. If the subsequent visit is missed or out-of-window, the end of the period will be the end
- of the day on the latest date that would be in-window for the visit. If a participant misses a vi, sit they will
- 206 be absent from the period begun by that visit. Participants must provide CGM data for at least 75% of the
- 207 time period to be included in the plots and tabulations for that time period.
- 208 7 Safe ty Analyses
- 209 Hierarchical safety endpoints will be analyzed according to the directions in 6.1. All safety endpoints
- 210 listed in 5.1 will be summarized in tables. Details of each reportable adverse event will be provided in a
- 211 listing.

212 8 Intervention Adherence

- 213 The following will be tabulated for the 8-weekstudy period to assess intervention adherence:
- PercenttimeofCGMsensoruse
- Percent time of closed-loop system use
- Percent time in different operational modes
- Percent of Al recommendations that are accepted without any study physician adjustments
- 218
- o For Al recommendations that are adjusted, tabulation of initial and adjusted values

219 System use metrics will be calculated from the beginning of study pump useuntil the end of the day

before the 8-Week visit date or the end of the 59th day after the date of the Closed Loop Initiation visit-

whichever is earlier. For participants who do not complete the study these metrics will be prorated: the

date of the final contact will be used in place of the 8-Week visit date.

223 9 Protocol Adherence and Retention

- 224 The following tabulations and analyses **will** be performed to assess protocol adherence for the study:
- Number of protocol and procedural deviations
- Flowchart accounting for all enrolled participants
- Flowchart of all participants at all scheduled visits and phone contacts after treatment initiation
- Number of and reasons for unscheduled visits and phone calls

JAEBCENTER FORHEALTH RESEARCH

- Number of participants who stopped treabnent and reasons

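### SAP 6.4 runs an adaptation period to the end of the visit window even when the next visit took place before the window opened, so days on new settings appear under the old ones and again in the next period

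*SAP*

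**What the plan says.** Protocol 8.12 and SAP 6.4 plan tables, 24-hour profiles and boxplots by adaptation period. In the protocol, the CGM-"measured outcomes listed in section 8.4.2 will be generated for each of the six adaptation periods and the" two 4-week periods.

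SAP 6.4 then sets the boundaries:

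- **Periods 1–5, normal case.** They "include data from the adjustment of pump settings at the visit until the adjustment of pump settings at the" following visit.
- **Periods 1–5, exception.** "If the subsequent visit is missed or out-of-window, the end of the period will be the end", continuing "of the day on the latest date that would be in-window for the visit".
- **Who is left out.** Only a participant who misses a visit will "be absent from the period begun by that visit".
- **Period 6.** Its end is fixed separately, as the day before the 8-Week visit or day 59, whichever comes first. That date closes the data "of the sixth adaptation period, which will begin at the 6-Week visit".
- **Completeness.** "Participants must provide CGM data for at least 75% of the" period to be shown for it.

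Protocol 3.3.1 and 3.3.2 apply updated settings at each scheduled visit before week 8. Protocol Table 4-1 gives windows of ±1 day (3-day visit), ±2 days (1- and 2-week visits) and ±4 days (4- and 6-week visits).

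Settings can also change between scheduled visits. Protocol 3.3.4 states: "During an unscheduled visit, the study investigator may elect to request an off-cycle optimization of pump" settings. Protocol Table 1 allows a manual adjustment for a safety issue at an unscheduled visit. SAP 6.4 mentions neither.

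**The concern.** The exception treats every out-of-window visit alike, but the two directions differ. When a visit is missed or late, the child is still on the old settings at the end of the window, so stopping there keeps the period clean. When a visit comes before the window opens, the settings change on that day. Carrying the old period to the end of the window fills its later part with glucose measured under the new settings.

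The early visit was held, so the rule on missed visits does not remove the child from the next period. That period starts at the actual adjustment, and the two periods share days. The 75% rule checks how complete the CGM data are and does nothing about the overlap.

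What is at stake is the step-by-step picture of glucose across successive AI adjustments. AI-driven adaptation is what the trial studies, and with about 30 children a few misassigned periods could shift a period's summary or boxplot. A programmer who follows the text exactly would produce the overlap.

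**Working it through.** The plan gives no figure to reproduce. The check applies the SAP 6.4 rule to the protocol's visit windows.

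**Inputs.** Target days 0 (initiation), 3, 7, 14, 28 and 42 start six periods, which matches the SAP's count. From Table 4-1 the windows are days 2–4, 5–9, 12–16, 24–32 and 38–46.

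**Assumptions.** The previous visit falls on its target day, visits take place at midday, and the end of day d is time d + 1. The early visit is placed one day before its window opens.

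**Formulas.**

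- Start = previous target day + 0.5
- Change = early visit day + 0.5
- End = last in-window day + 1
- Period length L = End − Start
- Days on new settings, also in the next period: O = End − Change
- Share = O / L

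| Next visit | Held on day | Start | Change | End | L | O | Share |
|---|---|---|---|---|---|---|---|
| 3 days | 1 | 0.5 | 1.5 | 5 | 4.5 | 3.5 | 78% |
| 1 week | 4 | 3.5 | 4.5 | 10 | 6.5 | 5.5 | 85% |
| 2 weeks | 11 | 7.5 | 11.5 | 17 | 9.5 | 5.5 | 58% |
| 4 weeks | 23 | 14.5 | 23.5 | 33 | 18.5 | 9.5 | 51% |
| 6 weeks | 37 | 28.5 | 37.5 | 47 | 18.5 | 9.5 | 51% |

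**Sensitivity.** Counting whole days instead gives 6/10 = 60%, 10/19 = 53% and 10/19 = 53% for the last three rows. A visit two days before its window gives 6.5/9.5 = 68% at 2 weeks and 10.5/18.5 = 57% at 4 and 6 weeks.

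**Contrast cases for the 4-week visit.**

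- Day 24, early but in window: the period ends at the adjustment, with L = 24.5 − 14.5 = 10.0 days and O = 0.
- Day 33, one day late: the period ends at time 33, with L = 18.5 days, all on the old settings. The 0.5 day up to the visit falls in no period.

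**Comparison within SAP 6.4.** The first 4-week period ends at the settings adjustment of the 4-Week visit, with no window exception. For a visit on day 23, that period stops on day 23 while the 2-to-4-week adaptation period runs to the end of day 32. The section therefore uses two boundaries for one event.

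**Settings change at an unscheduled visit.** Take a change on day 35 within a period from day 28 to day 42. The share on the newer settings is (42 − 35)/(42 − 28) = 7/14 = 50%. The next period still starts at the scheduled adjustment, so there is no overlap and each day is counted once.

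**The case against.** The strongest reply is that nothing inferential depends on these periods, and that stands. The outputs are descriptive. The hierarchical tests and 8-week metrics use the whole treatment period, the historical-control comparison has its own window, and the two 4-week periods do not use the exception. A reader might infer that doubled data enter a test or a standard error. They do not: the same days appear in two adjacent displays.

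A second reply is that the rule was probably written with late visits in mind. That may be so, but the SAP does not say it. Treating an early visit as missed would remove the overlap, but it would leave new-settings days in the old period, and the SAP names the two conditions separately.

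A reader might also infer that any early visit is affected. The documents do not support this: an early visit inside its window ends the period correctly.

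Nor should settings changes at unscheduled visits be grouped with the overlap. The SAP defines periods by visits and does not promise one set of settings per period, so a visit-to-visit description that includes what happened in between is a legitimate choice. Those days are counted once.

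Finally, these are not the only outputs bearing on change over time. The two 4-week periods give a coarser view that this rule does not affect.

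**Conclusion.** As written, SAP 6.4 misassigns data in adaptation periods 1–5 when the next scheduled visit is held before its window opens, and no other passage corrects it. Within an affected child's preceding period, about half to three-fifths of the days (2-, 4- and 6-week visits) or about four-fifths (3-day and 1-week visits) are on the new settings and also appear in the next period.

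These shares assume a visit one day before its window and the previous visit on target. They are not the effect on a summary across about 30 children, because the documents do not say how often visits fall before their windows. The consequence is limited to the period tables, 24-hour profiles and boxplots. It does not touch any hypothesis test, but the wording should be corrected.

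A separate and lesser point is that a settings change at an unscheduled visit can put two sets of settings in one period without any flag. That calls for transparency in reporting and is not an error in the period definition.

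**What to change.** In SAP 6.4, end each of periods 1–5 at the earlier of:

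- (a) the actual settings adjustment at the next scheduled visit, in or out of window; and
- (b) the end of the latest in-window day for that visit.

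This leaves the handling of in-window, late and missed visits as it is and changes only the visit held before its window. The overlap becomes zero in every row of the table. For a 4-week visit on day 23, the preceding period becomes 23.5 − 14.5 = 9.0 days, all on the old settings, instead of 18.5. Apply the 75% CGM rule to the resulting period.

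The cost is one sentence. The SAP already needs the adjustment times to bound its periods. The downside is a few shorter periods, some perhaps too short to be informative.

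For settings changes at unscheduled visits, whether off-cycle optimisations or manual safety adjustments, keep the visit-to-visit period, flag it, and report how many periods are flagged. Do not drop the data after the change: such visits may reflect how the child was doing, so truncating there would be informative. Confirm that the dates of these changes are captured. Protocol 3.2.1 says that recommended and approved settings are recorded on the Portal but does not mention dates or manual changes.
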